6. DESCRIPTION OF THE DISEASE IN THE STUDY

Ischemic Heart Disease and General Information on Coronary Angiography

The selection of eligible patients is based on the review of hospital registries and the analysis of coronary angiography procedures performed from January 2010 to December 2024.

Participants with suspected CAD undergo coronary angiography as part of the standard diagnostic and therapeutic pathway, in accordance with current guidelines for the management of ischemic heart disease. A patient is considered eligible if at least one mild or intermediate coronary stenosis is identified on angiographic assessment and subsequently evaluated with a coronary physiology test (fractional flow reserve [FFR] or angiography-derived FFR). These functional assessments guide the operator's decision to proceed with or defer vessel revascularization.

If a physiological evaluation of CAD is performed, the corresponding data — including FFR and/or angiography-derived FFR — are collected and recorded. The initial angiogram of all patients will be stored, anonymized, and kept locally for functional analysis (acceptable formats include CD, DVD, or digital files).

7. ENDPOINTS

Primary Endpoint

The primary endpoint is the composite risk of vessel-oriented composite endpoint (VOCE), including target vessel revascularization (TVR), vessel-related myocardial infarction (MI), and cardiovascular death.

Secondary Endpoint

- Individual components of the primary endpoint.
- Hospitalization for unstable angina.
- Angina status assessed using the Seattle Angina Questionnaire (SAQ). The SAQ will be used to evaluate patients' quality of life and the impact of angina symptoms over time. Scores from the main subscales (physical limitation, angina stability, angina frequency, treatment perception, and overall quality of life) will be analysed to correlate symptom severity with coronary physiology parameters (e.g., FFR/angiography-derived FFR).
- Number of prescribed antianginal drugs. The number of prescribed antianginal medications will be monitored to assess the intensity of pharmacological treatment required during follow-up. This parameter will serve as a proxy for residual disease severity and will allow comparison between patients managed conservatively and those treated with invasive interventions.

[figure not shown]

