Exclusion Criteria	
- Inability to provide informed consent to participate in the study
Informed Consent	Patients identified as eligible for the protocol will be invited to provide informed consent for participation in the retrospective study through contact by telephone, e-mail, mail, or during an outpatient visit.
Study Procedures	Once eligibility for the protocol is confirmed, informed consent is requested and obtained. After enrolment, the angiographic images from the index coronary angiography are analysed by the investigators. Long-term follow-up is performed by monitoring the clinical status and recording major adverse cardiac events through review of medical records, outpatient visits, or telephone contacts.
Primary Endpoint	Composite of vessel-oriented composite endpoint (VOCE), including target vessel revascularization (TVR), target vessel-related myocardial infarction (MI), and cardiovascular death.
Secondary Endpoints	
- Individual components of the primary endpoint- Hospitalization for unstable angina- Angina status (Seattle Angina Questionnaire)- Number of prescribed antianginal medications
Study Duration	Patients are retrospectively enrolled from January 2010 to December 2024. Clinical contact (medical records, outpatient visits, telephone communication) is periodically collected recording longitudinal data at 12-month intervals.
Clinical Event Adjudication Committee	The following events are adjudicated by an independent committee blinded to clinical data: TVR, target vessel-related MI, cardiovascular death, and hospitalization for unstable angina.

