2. INTRODUCTION

Integrated assessment of lesion hemodynamic impact and high-risk plaque features: an unmet clinical need.

Coronary artery disease (CAD) is one of the leading causes of morbidity and mortality in developed countries [1]. Coronary angiography remains the gold standard for diagnosing CAD, however, its ability to differentiate ischemic from non-ischemic lesions is limited [2]. Relying solely on the anatomical evaluation through coronary angiography fails to reveal the hemodynamic significance of epicardial CAD [3]. The 2-dimensional representation of the arterial lesion provided by angiography is limited in distinguishing intermediate lesions that require stenting from those that simply need appropriate medical therapy [4]. In the current era of drug-eluting stents (DES), when percutaneous coronary revascularization is achieved with high success rates, low complication rates, and excellent long-term patency, it might be tempting to treat all suspect lesions with DES implantation [4]. However, procedural complications associated with percutaneous coronary intervention (PCI), the inherent risk of restenosis, and late stent thrombosis still exist.

Histopathological studies have demonstrated that angiographic evidence of stenosis is usually not detected until the plaque's cross-sectional area approaches 40% to 50% of the vessel's total cross-sectional area. The outer wall of the artery, encompassed by the external elastic membrane, enlarges to accommodate the growing plaque. This process of compensatory dilatation seems to be limited. When the plaque area exceeds 40% to 50% of the external elastic membrane area, the plaque begins to encroach upon the lumen. Only at this point the angiogram might reveal minimal luminal narrowing [4–7].

In this respect, coronary physiology, which consider the functional severity of coronary stenosis, outperforms the traditional diagnostic approach based solely on morphometric assessment.

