4. STUDY OBJECTIVES

Primary Objective

The primary objective is to identify a risk profile for vessel-oriented composite endpoint (VOCE) associated with the functional characteristics of coronary lesions documented during coronary angiography.

Secondary Objectives

Secondary objectives include:

- Assessing the prognostic value of physiological parameters (invasive FFR and angiography-derived FFR).
- Analysing the clinical, demographic, and angiographic characteristics of patients with coronary lesions evaluated by coronary physiology to identify high-risk subgroups.
- Investigating the correlation between coronary physiology values and angina symptoms.
- Comparing invasive FFR with angiography-derived FFR.
- Comparing clinical outcomes between patients managed conservatively and those undergoing invasive interventions.

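### The antianginal drug count cannot be read as residual disease severity when conservative and invasive management are compared

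*Protocol*

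**What the plan says.** The protocol's synopsis lists "Number of prescribed antianginal medications" among the secondary endpoints. Section 7 explains the endpoint in two steps. It first describes the count as a measure of treatment: "The number of prescribed antianginal medications will be monitored to assess the intensity of pharmacological treatment required during follow-up". It then gives the count a second meaning and a use: "This parameter will serve as a proxy for residual disease severity and will allow comparison between patients managed conservatively and those treated with invasive interventions".

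The comparison belongs to a secondary objective in Section 4: "Comparing clinical outcomes between patients managed conservatively and those undergoing invasive interventions". Section 6 says how the two groups come about: "These functional assessments guide the operator's decision to proceed with or defer vessel revascularization". Section 8 repeats that the physiology result guided the treat-or-defer decision.

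The direct symptom measure, the SAQ, is also a secondary endpoint in Section 7. Its stated use is different: its subscale scores "will be analysed to correlate symptom severity with coronary physiology parameters". The drug count is the only endpoint in Section 7 whose text names the comparison of conservative with invasive management.

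**The concern.** Section 7 treats one number both as the intensity of drug treatment and as the severity of the disease that remains. Within a group of patients managed alike, the two may move together. Across two groups defined by how they were managed, they need not, because the number of drugs prescribed is partly a feature of the management.

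Take a deferred patient free of angina on two drugs and a revascularised patient with angina on one. The count ranks the first as having more residual disease, although the second is the one with symptoms.

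What is at stake is a secondary conclusion. A report that follows Section 7 would present a difference in prescribing habit or indication as a difference in residual disease between the two strategies.

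**Working it through.** The protocol gives no figure for this endpoint, so there is nothing to reproduce. The check sets the relevant sections side by side and then gives an illustration on assumed inputs.

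**1. Is the count separate from management?**
- Section 7 itself calls the count the intensity of treatment required.
- The introduction (Section 2) calls angiography "limited in distinguishing intermediate lesions that require stenting from those that simply need appropriate medical therapy", so drug treatment is the named alternative to stenting, though antianginal drugs are not mentioned there.
- The definition of ischemia-driven target vessel revascularization in Section 15 requires angina that persists under optimal medical therapy, so drug treatment is presumed to come before a revascularization that counts.
- The count is therefore partly a record of management.

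**2. Are the groups comparable at the outset?** No. Sections 6 and 8 say that the physiology result guided the decision. Patients who were deferred and patients who were treated differ in the ischaemic burden that also drives prescribing.

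**3. Is the direction of the error known?** No.
- Deferred patients may receive more antianginal drugs because drugs are what remains, which would make the conservative group look worse.
- Deferred patients may have lesions that do not cause ischaemia and need few such drugs, which would make the invasive group look worse.

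**4. Does another section repair this?**
- Section 12 handles confounding with Cox models. These fit times to event, not a drug count.
- Section 12 also names linear regression for correlations. Covariate adjustment would not remove the overlap between management and outcome.
- Section 13 acknowledges the lack of randomization and possibly uneven risk factors, but not that this endpoint is itself part of management.

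**5. Illustration (assumed inputs).** Suppose residual severity is identical in the two groups and the mean count differs by d drugs only because of prescribing policy. Assumed: SD 1.0 drug and a two-sided 0.05 test (Section 12 gives 0.05 without sidedness). The totals of 1,000 and 1,200 are the ends of the range in Section 11. The splits are assumed.

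SE = SD × √(1/n₁ + 1/n₂), and the probability of a significant result is approximately Φ(d/SE − 1.96).

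| Total (split) | SE | d = 0.1 | d = 0.2 | d = 0.3 |
|---|---|---|---|---|
| 1,000 (500/500) | 0.0632 | 0.35 | 0.89 | 1.00 |
| 1,000 (700/300) | 0.0690 | 0.31 | 0.83 | 0.99 |
| 1,200 (600/600) | 0.0577 | 0.41 | 0.93 | 1.00 |

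Example, 700/300 and d = 0.2: SE = √(1/700 + 1/300) = 0.0690; 0.2/0.0690 = 2.90; Φ(2.90 − 1.96) = 0.83. The result is the same with the sign of d reversed.

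**The case against.** **The protocol never says that antianginal drugs are the conservative treatment.** This stands. A reader might infer that in the conservative group these drugs simply are the treatment, so that the contrast is circular and the endpoint measures the exposure. The documents do not support that. Conservative management is not defined. The introduction speaks only of medical therapy, as general background, and where it describes drug therapy in detail it names lipid-lowering drugs. The exposure is the decision to revascularise or defer. The count is a separate variable that can vary within either group, and it remains a legitimate measure of drug burden.

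**A bias against conservative management should not be presumed.** This also stands, for the reason in step 3 of the working. It does not rescue the proxy, because a measure whose sign cannot be interpreted is no better suited to the comparison.

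**Section 7 already calls the count treatment intensity, and the SAQ is collected as well.** True, but the next sentence adds the severity reading and ties it to the management comparison, while the SAQ is tied to physiology values.

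**The missing baseline count is analysis detail.** Accepted. A statistical analysis plan may fix it, and the activity summary and flowchart are not shown, so whether index medication is collected cannot be judged. The point rests on the interpretation that Section 7 states, not on that absence.

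**The illustration proves no difference exists.** Also accepted. It shows only that a small prescribing difference, if present, would probably be declared significant at this sample size.

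**Conclusion.** The concern holds in a limited form. Section 7 fixes an interpretation that the design cannot support: a between-group difference in antianginal drug count cannot be read as a difference in residual disease severity, in either direction. The reasons are confounding by indication and the overlap of management with outcome, and nothing else in the protocol deals with that overlap.

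The actual size of the distortion cannot be derived from the documents. The probabilities of 0.83 to 0.93 for a 0.2-drug difference depend on an assumed SD, assumed splits and an assumed difference. The conclusion does not depend on them, since it follows from how the groups and the count arise.

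The reach is one secondary endpoint and the secondary objective it serves. The primary endpoint, the primary objective and the sample size are unaffected.

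**What to change.** In Section 7:

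- Delete the statement that the count is a proxy for residual disease severity for the comparison of management groups. Report it as treatment intensity (drug burden), as the preceding sentence already describes it.
- Base any between-group statement about residual symptoms on the SAQ scores, shown alongside the drug count from the same contact where both are available.
- If a change in count is reported, take the regimen recorded before the index procedure as the reference where available. The discharge regimen already reflects the treat-or-defer decision, so using it could absorb part of the difference being compared.

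The cost is mainly a wording change, plus abstraction of the pre-procedure regimen from medical records if a change is reported. The drug count would no longer support a severity claim between groups. SAQ scores may be missing for earlier follow-up taken from records, since index procedures go back to 2010 and the protocol is dated March 2025. Patients without a recorded pre-procedure regimen would drop out of any change analysis.

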8. PLANNED PROCEDURES AND DATA COLLECTION

The VR-CP study is a retrospective observational study enrolling consecutive patients who underwent coronary angiography for suspected ischemic heart disease and were found on angiographic examination to have coronary lesions evaluated using coronary physiology testing (FFR or angiography-derived FFR). These physiology assessments guided the decision to proceed with or defer target vessel revascularization.

Regardless of whether the lesion was treated invasively or managed conservatively, patients' clinical status and any adverse events are periodically recorded.

[figure not shown]
This retrospective follow-up is conducted through the collection of information from medical records, direct contact during outpatient visits, or via telephone communications, in order to ensure longitudinal data collection at 12-month intervals.

Fig. 1
Summary of Activities Performed

Flowchart

Fig.2 Retrospective Observational Study Design

*at the time of index procedure

DATA MANAGEMENT AND PROCEDURES TO ENSURE DATA CONFIDENTIALITY

The Sponsor commits to comply with Privacy Laws (as defined below), including provisions relating to security measures and confidentiality. The Sponsor guarantees, for itself and the Investigator, full awareness of all obligations arising from any applicable regulations concerning professional medical confidentiality and the protection of patients' personal data, including but not limited to EU Regulation 2016/679, the Italian Privacy Code (Legislative Decree 196/03, as amended), the provisions, guidelines, and current general authorizations issued by the Italian Data Protection Authority (collectively "Privacy Laws"). The Sponsor ensures that all personnel involved in the conduct of the study comply with Privacy Laws and the Sponsor's instructions regarding the protection of personal data, including security and confidentiality aspects. This obligation includes, for example: (i) providing the patient with a complete and lawful privacy notice (in particular, EU Regulation 2016/679, Legislative Decree 196/2003 as amended, and the aforementioned guidelines dated July 24, 2008); (ii) obtaining the patient's written informed consent before participation in the study; (iii) respecting the privacy rights of each data subject as established by applicable Privacy Laws; (iv) adopting all appropriate physical, logical, organizational, technical, and IT measures in compliance with applicable Privacy Laws. Due to the particular sensitivity of the data processed in the study, specific technical measures have been adopted to increase data security, without prejudice to any other minimum measures. These relate especially to the recording of data on persons involved in the study at the investigative sites, whether electronic or paper-based, their electronic transfer to a centralized database held by the Sponsor or third parties performing data validation and statistical processing on behalf of the Sponsor, and the management of this database. The Sponsor has taken appropriate measures to protect the recorded data from risks of unauthorized access, theft, or partial or total loss of paper documents, storage media, or fixed or portable processing systems.

Access to computers storing the data requires a username and password. Furthermore, access to the database for data entry sessions is protected by username and password. To ensure data confidentiality and to prevent data manipulation or loss, the following precautions are taken: Data access is restricted to authorized members only. The network is protected by a firewall. Internet connections are encrypted with a digital certificate (SSL technology). The database is hosted on a password-protected server, with passwords changed periodically. Database access is password protected and limited to responsible personnel at the center. Periodic backups are performed.

Paper materials related to clinical assessments will be stored in locked cabinets, with keys held only by persons authorized by the study management. The Sponsor has adopted secure communication protocols based on cryptographic standards for the electronic transmission of data collected from investigative sites to the centralized database maintained by the Sponsor or third parties performing subsequent data validation and statistical processing. The Sponsor will require the adoption of secure communication protocols for the transmission of any paper documentation. Regarding the database, appropriate authentication and authorization systems are in place according to user roles and access needs, along with periodic procedures to verify the quality and consistency of authentication credentials and authorization profiles assigned to data handlers. The Investigator will adequately dissociate patient identifying data from study result data (e.g., by anonymizing results using randomly generated alphanumeric codes) so that only pseudonymized data are processed by the Sponsor.

The Sponsor will allow access to clinical data (including medical records) and any other information relevant to the study, always in compliance with applicable Privacy Laws and respecting data security and confidentiality measures. Within the limits provided by the information given to study patients, personal data will be accessible only to employees, collaborators, monitors,

and auditors of the Sponsor, and/or to competent authorities in the exercise of their functions. The Sponsor and Investigator commit to clearly and fully inform each study patient about the processing of their personal data before participation in the study, according to applicable Privacy Laws. Before data acquisition, the Investigator will provide appropriate information to each patient regarding the nature, purpose, outcomes, consequences, and risks of the study. Prior to patient enrollment, the Investigator or authorized delegate will obtain written informed consent from the patient for: (a) participation in the study; (b) communication of related confidential information; (c) processing of personal data; (d) transfer of documentation containing the patient's personal data, including sensitive health data, to the Sponsor and/or competent authorities and/or other institutions, including those outside the European Union, in accordance with legal requirements and applicable Privacy Laws. The Sponsor commits to retaining original paper documentation (e.g., informed consent forms) for at least 7 years in compliance with Legislative Decree 200/2007.

10. STUDY DURATION

Recruitment: Once eligibility for the protocol is confirmed, informed consent is requested and obtained, and the patient is then enrolled in the study.

Patient involvement: Enrollment includes patients undergoing coronary angiography from January 2010 to December 2024.

Follow up: Follow-up will be maintained until all patients have completed a clinical evaluation at 10 years.

11. SAMPLE SIZE CALCULATION

In contemporary clinical trials on coronary physiology indices, the composite adverse event rate at 12 months follow-up is relatively low, ranging from 6.1% in the SWEDEHEART-IFR study to 6.7% in the DEFINE-FLAIR study. Therefore, assuming a type I error of 0.05 and a statistical power of 80%, the study should include 1000–1200 patients to generate a sufficient number of evaluable events. This sample size will also allow for subgroup analyses stratifying lesions by functional severity based on FFR values.

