1. SYNOPSIS

Study title	Verona coronary physiology interventional registry (VR-CP)
Protocol version	V1
Date	March, 1 st 2025
Study sponsor	Azienda Ospedaliera Universitaria Integrata di Verona
Study principal investigator	[name] MD PhD
Patient population	The observational Verona Coronary Physiology Interventional Registry (VR-CP) study enrolls patients with suspected coronary artery disease who underwent coronary angiography with functional assessment (coronary physiology).
Primary objective	The primary objective is to assess the functional characteristics of coronary lesions documented during coronary angiography and correlate them with the risk of cardiovascular events during follow-up.
Secondary objective	
- To examine the prognostic value of physiological parameters (FFR and angiography-derived FFR).- To analyze the clinical, demographic, and angiographic characteristics of patients with coronary lesions assessed by coronary physiology parameters, in order to identify high-risk subgroups.- To correlate coronary physiology values with angina symptoms.- To compare invasive FFR with angiography-derived FFR.- To compare clinical outcomes between patients managed conservatively and those undergoing invasive interventions.
Study design	The VR-CP study is a single-center observational study enrolling consecutive patients with coronary stenoses documented during coronary angiography and functionally assessed with coronary physiology (fractional flow reserve [FFR] or angiography-derived FFR) performed for suspected ischemic heart disease. Follow-up is conducted, after obtaining informed consent, through telephone contact and/or outpatient visits. Adverse events are adjudicated by an independent clinical events committee, blinded to clinical data.
Data source	The selection of eligible patients is extracted from registries and the analysis of coronary angiographic studies performed from January 2010 to December 2024.
Sample size	Enrollment will include approximately 1,000 patients evaluated with FFR or angiography-derived FFR. This sample size will allow for subgroup analyses stratifying lesions by functional severity based on FFR values.
Inclusion criteria	
- Coronary angiography with functional assessment by FFR or angiography-derived FFR (index procedure)- Provision of written informed consent- Age \geq18 years old at the time of the index procedure

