5. POPULATION

Inclusion Criteria

- Previous coronary angiography with assessment of FFR and/or angiography-derived FFR.
- Age \geq 18 years old*
- Provision of written informed consent.

* At the time of the index coronary angiography.

Exclusion Criteria

- Inability to provide informed consent to participate in the study.
- Age $<$ 18 years old*

* At the time of the index coronary angiography.

Vulnerable Populations

The following subjects will not be eligible for inclusion:

- Pregnant women
- Women who are breastfeeding

Criteria for Early Withdrawal from the Study

Subject's request to withdraw participation

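### Only patients alive to give consent from March 2025 can enter, so VOCE and cardiovascular-death risks counted from index will be too low, and the 12-month trial rates in Section 11 do not carry over

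*Protocol*

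**What the plan says.** **Sizing.** Section 11 (Sample Size Calculation) notes that "the composite adverse event rate at 12 months follow-up is relatively low", gives 6.1% and 6.7% from two trials of physiology indices, adds a type I error of 0.05 and 80% power, and concludes that "the study should include 1000–1200 patients to generate a sufficient number of evaluable events".

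**Who may enter.** Section 5 (Population) lists "Provision of written informed consent" as an inclusion criterion and "Inability to provide informed consent to participate in the study" as an exclusion criterion. The Synopsis says "Patients identified as eligible for the protocol will be invited to provide informed consent for participation in the retrospective study". Section 10 (Study Duration) fixes the order: "informed consent is requested and obtained, and the patient is then enrolled in the study".

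**Dates.** Section 10: "Enrollment includes patients undergoing coronary angiography from January 2010 to December 2024". The Synopsis dates version V1 "March, 1 st 2025".

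**Endpoint and analysis.** Section 7 makes cardiovascular death one of three VOCE components and, through the list of individual components, a secondary endpoint. Section 12 plans Kaplan-Meier curves, log-rank tests and Cox models, with the primary analysis on all events up to database lock.

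**Bias.** Section 13 accepts that retrospective enrolment can introduce selection bias, then says that enrolling consecutive patients keeps it to a minimum. It does not mention that patients must be alive to consent.

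**The concern.** Patients are identified from procedures up to 15 years old and must then sign a consent form. Anyone who died in between cannot sign, and the protocol describes no waiver, proxy or record-only route. The time from index to consent is therefore immortal time for every enrolled patient: a death in it would have kept that patient out of the study. Non-fatal events in patients who later died before contact are lost as well.

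Two things are at stake. First, event-free survival from index will look better than it was in the patients who had the procedure, for cardiovascular death and for VOCE, which contains it. Second, the rates quoted in Section 11 come from trials and are composite 12-month rates. To the extent that they include deaths, this cohort cannot reproduce them. Enrolling more survivors does not correct either problem.

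**Working it through.** **1. The plan's own figure.** The range of 1000–1200 cannot be derived from Section 11, which names no comparison, effect size, group split or required number of events. Its inputs give only the expected 12-month events at the trial rates:

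- 1000 × 0.061 = 61.0
- 1200 × 0.067 = 80.4

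**2. Gap from index to consent.** The earliest consent is taken as 1 March 2025, the protocol date.

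- Index window: January 2010 to December 2024 = 15 × 12 = 180 months.
- Longest gap: 1 January 2010 to 1 March 2025 = 182 months.
- Shortest gap: end of December 2024 to 1 March 2025 = 2 months.

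**3. Index months with no countable 12-month cardiovascular death.** The 12-month window closes before consent for every index date up to the end of February 2024.

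- January 2010 to February 2024 = 14 × 12 + 2 = 170 months.
- 170 / 180 = 94.4%.

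This needs no event rate. It is a share of calendar time and equals the share of patients only if accrual was even. A later start of consent raises it: with 1 June 2025 it is 96.1% by days.

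**4. Share of 12-month time that precedes consent** (assumption: even accrual). For the last 10 index months the gap falls from 12 to 2 months, a mean of 7.

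- L = (170 × 12 + 10 × 7) / (180 × 12) = 2110 / 2160 = 0.977.

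**5. Illustration of the effect on the 12-month rate.** The protocol does not give the cardiovascular-death share *s* of the composite, so a range is assumed. Also assumed: deaths evenly timed within the 12 months, and the cited trial rates taken as the VOCE rate. Events not observable = N × r × s × L; fall in the rate = r × s × L.

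| Assumed s | Not observable, N = 1000, r = 6.1% | Not observable, N = 1200, r = 6.7% | Fall in 12-month rate (points) |
|---|---|---|---|
| 10% | 6.0 of 61.0 | 7.9 of 80.4 | 0.60–0.65 |
| 20% | 11.9 of 61.0 | 15.7 of 80.4 | 1.19–1.31 |
| 30% | 17.9 of 61.0 | 23.6 of 80.4 | 1.79–1.96 |

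Two simplifications pull in opposite directions. The dead also leave the denominator, which raises the rate among the enrolled by a factor of at most 1 / (1 − 0.067 × 0.3 × 0.977) = 1 / 0.980, about 2%. Non-fatal events in patients who later died before contact are not included in the loss.

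**6. Relative effects.** A simulation used 60,000 eligible patients, a true VOCE hazard ratio of 2.0, *s* of 10–30%, and a cardiovascular-death hazard either unchanged or tripled after a non-fatal event. Among consenters the hazard ratio was 1.88–1.99. The value of 2.0 is only an example; the protocol states no hazard ratio.

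**The case against.** **The primary analysis is not a 12-month analysis.** Section 12 uses the entire follow-up to database lock, and Section 11 cites the 12-month rates as background. This stands. A reader might infer that 1000–1200 patients are too few, or that the 80% power is wrong. The documents support neither: no 12-month comparison or effect size is planned, events accumulate well past 12 months, and the power statement cannot be checked either way. Nor does it follow that no cardiovascular deaths will be seen, because those after consent count. Longer follow-up does not bring back the deaths before consent, however.

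**The primary objective is a relative one.** Section 4 seeks a risk profile associated with lesion function, and the hazard ratio is little disturbed in the simulation. This also stands. The harm is mainly to absolute risks and to cardiovascular death as an endpoint in its own right.

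**Long-term losses depend on how Section 10 is read.** Follow-up until all patients have a 10-year evaluation may mean 10 years each, or observation of everyone until the last patient reaches 10 years. A 10-year loss figure would hold under only one reading, so none is given.

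**Section 13 already admits selection bias.** It does so in general terms. Consecutive identification cannot remove selection by survival to consent, because that selection acts after the consecutive list is drawn up.

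**Delayed entry belongs in an SAP.** The handling may. Who can be enrolled, what Section 11 rests on and what Section 13 claims are matters for the protocol.

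**Conclusion.** The point holds as a survivor-selection (left-truncation) problem, not as a sample-size error. From the documents alone, every enrolled patient has survived 2 to 182 months from index, and for 170 of 180 index months (94% of calendar time) the number of countable 12-month cardiovascular deaths is zero. If time at risk runs from index, the Kaplan-Meier risks of VOCE and cardiovascular death are biased downward, and the 6.1–6.7% rates do not describe this cohort.

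The 94% rests on the protocol date as the earliest consent date and on the absence of any stated route for deceased patients. The size of the fall in the 12-month rate, 0.6 to 2.0 points, also rests on the assumed 10–30% death share, even accrual, even timing of deaths, and trial composites equated with VOCE. The direction does not depend on those figures.

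**What to change.** 1. **Sections 5 and 10.** Ask the ethics committee whether eligible patients who died before contact may be included from hospital records. If approval is granted, amend the consent criteria. Cost: an amendment and a record review, with no visits. This is the better remedy because it restores the missing deaths and the non-fatal events that preceded them.

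2. **Section 12, if approval is not granted.** State that:
   - cardiovascular death is analysed with delayed entry at the consent date on the time-from-index scale;
   - VOCE is analysed the same way at least as a sensitivity analysis, with non-fatal events before consent reported separately;
   - any risk counted from index is described as conditional on survival to consent.

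   Cost: one added date in the eCRF and fewer usable events. The first year after index would be thinly covered: on the even-accrual assumption only 1 − 0.977 = 2.3% of 12-month time falls after the earliest consent. Removing all pre-consent non-fatal events from the only VOCE analysis would be a real trade-off in a retrospective study, hence the sensitivity role.

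3. **Section 11.** Say that the 12-month trial rates include deaths that this cohort cannot contribute, and base the expected number of events on the entire follow-up actually analysed. Cost: text only.

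4. **Section 13.** Replace the claim that consecutive enrolment minimises selection bias with a plain statement of the survivor selection. Commit to reporting how many patients were eligible, dead before contact, not reached and refusing. Cost: a screening log.
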